### **6.2.9. End of Study Treatment Visit (21 days after last dose)**

At the end of study treatment, the following procedures will be performed.

- Physical examination
- Vital signs
- Weight
- ECOG Performance Status (Section 10.1)
- Perform an echocardiogram or MUGA scan
- Perform a 12-lead ECG
- Record concomitant medications and AEs
- Have subject complete the PRO assessments before any study-related procedures are performed
- Collect blood sample for CBC with differential and platelet count
- Collect blood sample for serum chemistries
- Collect urine sample for urinalysis (Section 9.7)
- Sparse PK: collect a blood sample for PK (Table 8.1)
- Collect blood sample for HAHA
- Perform a serum or urine pregnancy test for female subjects of childbearing potential
- Tumor measurement assessments unless it was performed within the previous 6 weeks or the previous assessment demonstrated disease progression
- Collect blood samples for additional biomarkers

If there is a significant clinical or laboratory abnormality in need of monitoring beyond the end-of-study treatment visit, subjects will be followed until resolution of the abnormality, until it is considered stable, or the subject begins another cancer treatment.

For subjects with positive HAHA at the end-of-study treatment visit, additional serum samples for HAHA and PK should be collected every 3 months until HAHA titers return to baseline or until the start of another cancer therapy. Samples will be collected up to 1 year from the last dose of study drug or collected up to the time that a subject starts another cancer therapy, whichever occurs first.

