## **9.9. Electrocardiograms**

A 12-lead ECG will be performed within 14 days prior to Screening, at the End-of-Study Treatment visit, and during the study at the discretion of the Investigator.

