### **11.6.4. Electrocardiogram Analyses**

The ECG parameters (PR, RR, QRS, heart rate-corrected QT interval by Bazett's or by Fridericia's formula) [QT, QTcB and QTcF]) will be summarized using descriptive statistics for actual values and for changes from baseline by treatment group by scheduled time of evaluation including end of treatment visit as well as for the maximum post treatment values.

The incidence of outliers in maximum absolute QTcF and QTcB intervals (> 450 > 480 and > 500 msec) and the maximum absolute uncorrected QT intervals (> 500 msec) over end-of-treatment evaluation, as well as in QTcF and QTcB maximum changes from baseline (> 30 and > 60 msec) over end-of-treatment evaluation will be summarized by treatment. A listing of ECG data will be provided.

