8.3.5. ECG

Values and change from baseline for ECG parameters, including heart rate, PR interval, RR interval, QRS duration, QT interval, QTcB ($QT / RR^{**1/2}$), and QTcF ($QT / RR^{**1/3}$), will be summarized for each treatment group and in total at scheduled time of evaluation (including end-of-treatment visit).

In addition, the following notable ECG interval values for each parameter will be evaluated:

QTcB and QTcF:

- New >450 msec
- New >480 msec
- New >500 msec
- Increase from baseline >30 msec
- Increase from baseline >60 msec

Note that “New” implies a newly occurring ECG abnormality. It is defined as an abnormal ECG finding at post-baseline that is not present at baseline, e.g., QTc New > 480 msec implies QTc > 480 msec post-baseline and QTc ≤ 480 msec at baseline.

A subject with multiple occurrences of a newly occurring abnormality is counted only once per abnormality.

The percentage of subjects with newly occurring qualitative ECG abnormalities is based on the total number of subjects who are at risk of developing this abnormality in the category. For each individual abnormal finding, this is defined as the number of subjects with both baseline and post baseline evaluations and a normal value at baseline.

If a QTc record is missing but the records of QT interval and RR are available then QTc should be derived using the formula above. If RR is missing but heart rate (HR) is available, QTc should be derived using the following formulae:

- $QTcF = QT \times (HR/60)^{1/3}$
- $QTcB = QT \times (HR/60)^{1/2}$

Data from ECGs will also be presented in the data listings using the Safety Analysis Set.

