9. CHANGES FROM THE PROTOCOL SPECIFIED STATISTICAL ANALYSES

No changes have been issued.

Approved

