Vital Sign (units) Visit	Patritumab+ cetuximab + cisplatin or carboplatin (N=xxx)		Placebo + cetuximab + cisplatin or carboplatin (N=xxx)		Total (N=xxx)	
	Result	Change	Result	Change	Result	Change
Systolic Blood Pressure (mm Hg)						
End of Treatment						
n	xx	xx	xx	xx	xx	xx
Mean	xx.x	xx.x	xx.x	xx.x	xx.x	xx.x
SD	xx.xx	xx.xx	xx.xx	xx.xx	x.xx	xx.xx
Median	xx.x	xx.x	xx.x	xx.x	xx.x	xx.x
Minimum	xx	xx	xx	xx	xx	xx
Maximum	xx	xx	xx	xx	xx	xx
Last Observation on Treatment						
n	xx	xx	xx	x	xx	xx
Mean	xx.x	xx.x	xx.x	xx.x	xx.x	xx.x
SD	xx.xx	xx.xx	xx.xx	xx.xx	xx.xx	xx.xx
Median	xx.x	xx.x	xx.x	xx.x	xx.x	xx.x
Minimum	xx	xx	xx	xx	xx	xx
Maximum	xx	xx	xx	xx	xx	xx
Maximum Post-baseline Value						
N	xx	xx	xx	xx	xx	xx
Mean	xx.x	xx.x	x.x	xx.x	xx.x	xx.x
SD	xx.xx	xx.xx	xx.xx	xx.xx	xx.xx	xx.xx
Median	xx.x	xx	xx.x	xx.x	xx.x	xx.x
Minimum	xx	xx	xx	xx	xx	xx
Maximum	xx	xx	xx	xx	xx	xx
Minimum Post-baseline Value						

Lab Test N (SI unit)

Notes: The baseline value is defined as the last non-missing value before initial administration of study treatment. Repeated or unscheduled tests are not summarized for each scheduled visit, but are included for summaries of last observation on treatment, maximum and minimum post-baseline values. The End of Treatment value is based on the CRF visit. Last observation on treatment is defined as the last non-missing value on or prior to end of treatment duration + 7.

Source Data: adam.advs; Listing 16.2.8.3.1.

Programming note: continue table for Diastolic Blood Pressure, Pulse Rate, Respiratory Rate, Body Temperature and Weight

Programming Note: continue for HRG Low and Overall on the next page

Daiichi Sankyo Pharma Development
Protocol U31278-A-U203

Page x of y

<programe> <run date time>

<Run Type> (Data Cut Date: DDMMYYYY; Data Extraction Date: DDMMYYYY)

Table 15.3.6.1: Summary of 12-Lead ECG and Change from Baseline
Safety Analysis Set

HRG High

Parameter (units)	Patritumab+ cetuximab + cisplatin or carboplatin (N=xxx)		Placebo + cetuximab + cisplatin or carboplatin (N=xxx)		Total (N=xxx)	
	Result	Change	Result	Change	Result	Change
Visit						
Heart Rate (bpm)						
Baseline						
n	xx		xx		x	
Mean	xx.x		xx.x		xx.x	
SD	xx.xx		xx.xx		xx.xx	
Median	xx.x		xx.x		xx.x	
Minimum	xx		xx		xx	
Maximum	xx		xx		xx	
End of Treatment						
n	xx	xx	xx	xx	xx	xx
Mean	xx.x	xx.x	xx.x	xx.x	xx.x	xx.x
SD	xx.xx	xx.x	xx.xx	xx.xx	xx.xx	xx.xx
Median	xx.x	x.x	xx.x	xx.x	xx.x	xx.x
Minimum	xx	x	xx	xx	xx	xx
Maximum	xx	xx	xx	xx	xx	xx

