Notes: The baseline value is defined as the last non-missing value before initial administration of study treatment. The End of Treatment value is based on the CRF visit

Source Data: adam.adeg; Listing 16.2.8.3.2.

Programming note: continue with PR interval, RR interval, QRS duration, QT interval, QTcB, and QTcF

Programming Note: continue for HRG Low and Overall on the next page

Daiichi Sankyo Pharma Development
Protocol U31278-A-U203

Page x of y

<programe> <run date time>

<Run Type> (Data Cut Date: DDMMYYYY; Data Extraction Date: DDMMYYYY)

Table 15.3.6.2: Summary of Subjects Meeting Pre-Specified QT and QTcB/QTcF Criteria
Safety Analysis Set

HRG High	Patritumab+ cetuximab + cisplatin or carboplatin (N=xxx) n (%)	Placebo + cetuximab + cisplatin or carboplatin (N=xxx) n (%)	Total (N=xxx) n (%)
Maximum Over All Post- Baseline Evaluations			
Subjects with at least one baseline and one post-baseline ECG evaluation	xx	xx	xx
QTcB			
New > 450 msec	xx (xx.x%)	xx (xx.x%)	xx (xx.x%)
New > 480 msec	xx (xx.x%)	xx (xx.x%)	xx (xx.x%)
New > 500 msec	xx (xx.x%)	xx (xx.x%)	xx (xx.x%)
Change from baseline >30 msec	xx (xx.x%)	xx (xx.x%)	xx (xx.x%)
Change from baseline > 60 msec	xx (xx.x%)	xx (xx.x%)	xx (xx.x%)
QTcF			
New > 450 msec	xx (xx.x%)	xx (xx.x%)	xx (xx.x%)
New > 480 msec	xx (xx.x%)	xx (xx.x%)	xx (xx.x%)
New > 500 msec	xx (xx.x%)	xx (xx.x%)	xx (xx.x%)
Change from baseline >30 msec	xx (xx.x%)	xx (xx.x%)	xx (xx.x%)
Change from baseline > 60 msec	xx (xx.x%)	xx (xx.x%)	xx (xx.x%)

Notes: The baseline value is defined as the last non-missing value before initial administration of study treatment. Percentages are based on the number of subjects in the Safety Analysis Set for each cohort with at least one baseline and one post-baseline ECG assessment. "New" means the category of the QTc abnormality was not present at baseline and became present at least one post-baseline ECG assessment.

Source Data: adam.adeg; Listing 16.2.8.3.2.

Programming Note: continue for HRG Low and Overall on the next page

<Run Type> (Data Cut Date: DDMMYYYY; Data Extraction Date: DDMMYYYY)

Table 15.3.7: Shift Table of ECOG Status
 Safety Analysis Set

HRG High

Time Point Treatment	Baseline ECOG PS	Post-Baseline ECOG PS						Total n (%)	Missing n
		0 n (%)	1 n (%)	2 n (%)	3 n (%)	4 n (%)	5 n (%)		
Cycle 1 Day 1									
Patritumab+ cetuximab + cisplatin or carboplatin (n=xxx)	0	xx (xx.x%)	xx (xx.x%)	xx (xx.x%)	xx (xx.x%)	xx (xx.x%)	xx (xx.x%)	xx (xx.x%)	xx

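### SAP 8.3.5 and the Table 15.3.6.1 shell omit, without declaring it, the maximum post-treatment ECG summary that protocol 11.6.4 plans

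*SAP*

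**What the plan says.** **Protocol 11.6.4** asks for descriptive statistics of PR, RR, QRS, QT, QTcB and QTcF, as actual values and as changes from baseline, "by scheduled time of evaluation including end of treatment visit as well as for the maximum post treatment values". It also plans counts of subjects whose maximum passes set limits: 450, 480 and 500 msec for QTcB and QTcF, 500 msec for uncorrected QT, and increases of 30 and 60 msec for QTcB and QTcF.

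**SAP 8.3.5** adds heart rate to the list and says that values and changes "will be summarized for each treatment group and in total at scheduled time of evaluation (including end-of-treatment visit"). It does not mention a maximum. Its notable-value criteria are for QTcB and QTcF only.

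**The Table 15.3.6.1 shell (SAP 11.4)** sets out heart rate with a baseline block and an End of Treatment block, then tells the programmer to "continue with PR interval, RR interval, QRS duration, QT interval, QTcB, and QTcF". Its footnote defines those two blocks and gives no rule for unscheduled ECGs.

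**ECG timing.** After the screening ECG, protocol 9.9 places ECGs "at the End-of-Study Treatment visit, and during the study at the discretion of the Investigator". The schedule of events (protocol Table 17.2) marks only screening and that end visit, and its footnote leaves any other ECG to the investigator. The end visit falls 21 days after the last dose in protocol 6.2.9, but within 21 days in protocol 4.1.5.

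**Declared changes.** Protocol 11.2 commits the SAP to describing departures from the planned analyses and the reasons for them. SAP 9 says: "No changes have been issued".

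**The concern.** The protocol names ECGs among its safety endpoints and planned a per-subject maximum for the continuous ECG parameters. The SAP drops that summary without saying so. Because the schedule fixes no ECG between screening and the end visit, the maximum was the only planned route by which an ECG recorded during dosing could reach the continuous table. Without it, the only post-baseline value there comes from a visit after the last dose of any study drug. If, say, PR or QRS lengthened during treatment and recovered by then, no summary table would show it; a reader would have to find it in the listing.

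**Working it through.** No arithmetic beyond counting applies, so the check sets the texts side by side.

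**1. Blocks required and blocks present in the continuous ECG summary**

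| Block | Protocol 11.6.4 | SAP 8.3.5 | Table 15.3.6.1 shell |
|---|---|---|---|
| Baseline | yes (needed for change) | yes | yes |
| End of Treatment | yes | yes | yes |
| Maximum post-treatment | yes | no | no |

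One block is missing for each parameter. The protocol names six parameters (PR, RR, QRS, QT, QTcB, QTcF). The SAP adds heart rate, so the shell covers 6 + 1 = 7.

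**2. ECGs that can reach the table.** Scheduled post-baseline ECGs: one, at the end visit. Scheduled ECGs during treatment: none. A discretionary ECG has no visit row, so it could enter only through the missing block.

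**3. What the missing block should contain.** SAP 8.3.2 speaks of maximum post-treatment values for laboratory tests, and the matching shell labels them maximum post-baseline, so I take the two terms as equivalent. The protocol does not say that unscheduled ECGs count towards the maximum. With one scheduled post-baseline ECG, however, a maximum over scheduled visits alone would simply repeat the End of Treatment value. The row adds information only if unscheduled ECGs count.

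**4. Neighbouring analyses.** SAP 8.3.2 (laboratory), 8.3.4 (vital signs) and 8.3.9 (LVEF) all summarize maximum and minimum values and include unscheduled tests in them; Tables 15.3.4.1, 15.3.5 and 15.3.8 follow. For LVEF, protocol 11.6.6 asked only for a listing, and the SAP went further. For ECG, the protocol asked for the maximum, and the SAP left it out. This looks like an oversight, though the documents do not say.

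**5. What other tables supply, by parameter**

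| Parameter | Continuous maximum (value and change) | Other maximum-based summary |
|---|---|---|
| QTcB, QTcF | none | Table 15.3.6.2: new values >450, >480, >500 msec and changes >30, >60 msec, by arm, over all post-baseline ECGs |
| Heart rate, RR | none from ECG | Table 15.3.5: maximum and minimum pulse rate, unscheduled tests included (the longest RR corresponds to the slowest rate) |
| PR, QRS | none | none |
| Uncorrected QT | none | none |

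So 7 of 7 parameters lack the continuous maximum. Of these, 2 have a categorical substitute and 2 a close proxy, leaving 7 − 2 − 2 = 3 with no maximum-based summary of any kind.

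**6. Uncorrected QT loses twice.** The protocol's count of maximum uncorrected QT above 500 msec is absent from SAP 8.3.5 and from the rows of Table 15.3.6.2, although that table's title mentions QT.

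**The case against.** A reader might infer that the whole arm comparison of ECG change rests on a single recording made three weeks after dosing ended, and that ECGs taken during treatment are lost to the analysis. The documents do not support that.

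- Table 15.3.6.2 compares the arms on QTcB and QTcF maxima over every post-baseline ECG, including changes from baseline above 30 and 60 msec. QTc change during treatment is therefore already summarized, in categories.
- SAP 8.3.5 also presents ECG data in the listings (Listing 16.2.8.3.2), so ECGs during treatment stay in the report.
- Three weeks is not a settled figure. Protocol 6.2.9 and protocol 4.1.5 differ, and under the latter 21 days is the outer limit.

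A reader might also suppose that the discretionary ECGs are the ones most likely to show a drug effect. Nothing in the documents says so. Their number and the reasons for ordering them will vary, so a per-subject maximum depends partly on how often ECGs were done. For a subject with no extra ECG, it equals the End of Treatment value. Restoring the block therefore honours the protocol but does not create systematic on-treatment ECG data; that limit comes from the visit schedule.

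Finally, SAP 8.3 plans no inferential analysis of safety data, so no test or efficacy result changes.

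All of this stands and narrows the point. None of it explains why a protocol-specified summary is missing or why SAP 9 is silent.

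**Conclusion.** The mismatch holds, as a minor one. The SAP text and shell omit the continuous maximum summary for all seven ECG parameters, six of which protocol 11.6.4 names, and SAP 9 does not declare the omission. As written, Table 15.3.6.1 contains no on-treatment value. The practical loss is greatest for PR, QRS and uncorrected QT, which have no maximum-based summary anywhere; uncorrected QT also loses its planned count above 500 msec. For QTcB and QTcF the loss is limited to the continuous form.

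This rests on two readings: that post-treatment maximum means the maximum after baseline, as in the SAP's laboratory analysis, and that discretionary ECGs are unscheduled and so have no visit row. How many such ECGs there will be cannot be known from the documents, so the size of the effect on the reported results cannot be given.

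**What to change.** 1. In Table 15.3.6.1, add a maximum post-baseline block (actual value and change from baseline) for every parameter, with the footnote used in Tables 15.3.5 and 15.3.8 so that unscheduled ECGs count towards it.
2. Amend SAP 8.3.5 to match protocol 11.6.4.
3. Restore the row for uncorrected QT above 500 msec in SAP 8.3.5 and Table 15.3.6.2.
4. If the omission was intended, state it with the reason in SAP 9 instead.
5. Reconcile the timing of the end visit between protocol 6.2.9 and protocol 4.1.5, so that the End of Treatment ECG can be interpreted.

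Minimum blocks for heart rate and RR would be a reasonable option but go beyond the protocol.

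The cost is one block per parameter in one table, one row in another and a short text edit, using ECG data already collected. The one downside is interpretive: the number of discretionary ECGs differs between subjects, so the maximum should be read descriptively.
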